5.1 Type of trial

This is a phase 3b, 16-week, multicentre, multinational, 1:1 randomised, double-blind, active controlled, treat-to-target, parallel group trial with a 12-week run-in period comparing the effect and safety of faster aspart to NovoRapid[®] both in combination with insulin degludec with or without metformin in subjects with T2DM treated with a basal-bolus regimen.

[figure not shown]

Figure 5–1 Trial Design.

The trial design is summarised in Figure 5–1. The total duration of the trial is approximately 34 weeks divided into the following periods:

- An approximately 2-week screening period
- A 12-week run-in period primarily for optimisation of the basal insulin and subject training
- A 16-week treatment period
- A 30-day follow-up period: FU1; 7 days after end of treatment and FU2; 30 days after end of treatment

The trial includes a screening period followed by weekly visits/phone contacts during the trial. At Visit 2, all eligible subjects will be enrolled in a 12-week run-in period. After the run-in period, subjects eligible for randomisation (HbA_{1c} \leq 9.0% measured at Visit 13) will be randomised (1:1) to receive double blinded treatment with either faster aspart or NovoRapid[®] both in combination with once daily insulin degludec with or without metformin.

Protocol		Date:	23 February 2018	Novo Nordisk
Trial ID: NN1218-4113	CONFIDENTIAL	Version:	4.0	
UTN: U1111-1180-0636		Status:	Final	
EudraCT no.: 2016-000878-38		Page:	22 of 112	

All subjects will have a standardised meal test at baseline (Visit 14 before randomisation) and at end of treatment (Visit 30). The meal test will be described in more details in section 8.3.1.

After the 16-week treatment period, each subject will have a 30-day safety follow-up period.

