6.2 Inclusion criteria

For an eligible subject, all inclusion criteria must be answered "yes".

- 1. Informed consent obtained before any trial-related activities. Trial-related activities are any procedures that are carried out as part of the trial, including activities to determine suitability for the trial.
- 2. Male or female, age \geq 18 years at the time of signing informed consent.
- 3. Diagnosed with type 2 diabetes mellitus ≥ 10 years prior to screening (Visit 1).
- 4. Treated with a basal-bolus insulin regimen ≥ 1 year prior to the day of screening (Visit 1). A basal-bolus insulin regimen is defined as basal insulin once or twice daily and bolus insulin analogue taken with meals at least 3 times daily. Treatment with premixed insulin or soluble insulin combination is not considered a basal-bolus regimen.
- 5. Treated with or without oral antidiabetic drugs including extended release formulations.
- 6. HbA_{1c} 7.0-10.0% (both inclusive) as assessed by central laboratory at screening (Visit 1).
- 7. Able and willing to adhere to the protocol including performance of SMPG profiles and meal test.
- 8. Able and willing to consume 3 main meals (breakfast, lunch and dinner) daily throughout the trial.

Page:

26 of 112

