8.3.3 Self-measured plasma glucose

At Visit 2, subjects will be provided with a BG meter including ancillaries as well as instructions for use, if needed. The subjects will be instructed in how to use the device.

The subjects should be instructed how to record the results of the SMPG values including a 7-9-7 point profile in the diaries. Data from the diary must be transcribed into the eCRF during or following the contact. If obtained via phone and a discrepancy is later detected, the values in the eCRF must be corrected.

Protocol		Date:	23 February 2018	Novo Nordisk
Trial ID: NN1218-4113	CONFIDENTIAL	Version:	4.0	
UTN: U1111-1180-0636	CONFIDENTIAL	Status:	Final	
EudraCT no.: 2016-000878-38		Page:	45 of 112	

Occasional review by the investigator of the values stored in the memory of the BG-meter and correct reporting of these in the diary is advised in order to ensure adequacy of the data reported in the trial database.

The BG meters use test strips calibrated to plasma values. Therefore, all measurements performed with capillary blood are automatically calibrated to plasma equivalent glucose values, which will be shown on the display.

Only the BG meter provided by Novo Nordisk should be used for the measurements required in the protocol.

4-point self-measured plasma glucose profile

The 4-point SMPG profile will be recorded for insulin titration purposes. Subjects will be instructed to perform 4-point profiles every day from Visit 2 to Visit 30 for titration purposes. The measurements should be performed at the following time points:

- Before breakfast
- Before lunch
- Before main evening meal (dinner)
- At bedtime

For SMPG measurements actual clock time, time point (e.g. before breakfast), date and value should be recorded in the diary.

SMPG values measured before breakfast, lunch, main evening meal, and at bedtime should be performed before any injection of bolus insulin and just before the start of the meal (breakfast, lunch or main evening meal). SMPG values measured before breakfast should be performed in a fasting condition. The 4-point profile is part of the 7- or 9-point profiles which are measured prior to selected site visits.

7-9-7 point self-measured plasma glucose profile

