The 7- and 9-point SMPG profiles will be used for titration purposes and evaluation of the effect of the trial. The subject will be instructed to perform a 7-9-7 point profile on the 3 consecutive days just before selected visits as outlined in the flowchart in section $\underline{2}$. See $\underline{\text{Table 8-2}}$ (7-point profiles indicated as X and the 9-point profile indicated as $\sqrt{ }$).

Protocol Da	Date: 23 February 2018	Novo Nordisk
-------------	------------------------	--------------

 Trial ID: NN1218-4113
 Version: 4.0

 UTN: U1111-1180-0636
 Status: Final Page: 46 of 112

Table 8–2 7-point SMPG profiles with additional 9-point SMPG profile

Time point	Day -3 7-point profile	Day -2 9-point profile	Day -1 7-point profile
Before breakfast	X	1/	√(X) ^a
60 minutes after the start of breakfast	X	1/	X
Before lunch	X	1/	X
60 minutes after the start of lunch	X	1/	X
Before main evening meal	X	1/	X
60 minutes after the start of main evening meal	X	1/	X
At bedtime	X	1/	X
At 4 am		1/	

^aThe last SMPG in the 9-point profile and the first SMPG of the 7-point profile on day-1 are overlapping.

For SMPG measurements actual clock time, time point (e.g. before breakfast), date and value should be recorded in the diary. SMPG values measured before breakfast, lunch and main evening meal and at bedtime should be performed before any insulin injection and just before the start of the meal (breakfast, lunch or main evening meal). SMPG values measured before breakfast should be performed in a fasting condition.

The measurements will be used to evaluate the glucose profile.

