A consequence of the pharmacodynamics of rapid-acting insulin analogues is that if hypoglycaemia occurs, it may occur earlier after an injection than with soluble human insulin. A phase 3A trial with faster aspart in T2DM showed a slight shift in distribution of the occurrence of hypoglycaemic episodes in relation to a meal when comparing to NovoRapid[®]. A statistical significant higher rate of hypoglycaemic episodes was seen during the first 2 hours after a meal for faster aspart. This is not unexpected and reflects the pharmacokinetic and pharmacodynamic properties of faster aspart. 22

All treatments are contraindicated in case of hypersensitivity to the active substances or any of the excipients. The risk of hypersensitivity is partly mitigated by excluding subject with known hypersensitivity towards any trials products or related products.

Injection site reactions can occur. The nature of the injection site reactions is expected to be mild, transient, and more of a visual character and is not expected to be of concern to the subject's safety. Lipodystrophy (including lipohypertrophy, lipoatrophy) at the injection site can occur. Continuous rotation of the injection site within the particular injection area may help to reduce the risk of developing these reactions.

The blood samples during meal tests might be inconvenient to the subjects, but are not of any safety concern.

Protocol		Date:	23 February 2018	Novo Nordisk
Trial ID: NN1218-4113	CONFIDENTIAL	Version:	4.0	
UTN: U1111-1180-0636		Status:	Final	
EudraCT no.: 2016-000878-38		Page:	99 of 112	

Subjects in this trial will be using bolus and basal insulin administered via two differently colour-coded prefilled pens. This colour difference will help the subject to distinguish between the pens and thereby minimise the risk of medication errors with regard to mixing up the pens used for basal and bolus injection. Subjects will be trained in distinguishing between the pens. It is expected that the risk of mixing up basal and bolus insulin in this trial is similar to other clinical trials.

No maximum dose of insulin is specified as doses are titrated individually. All subjects will perform 4-point profiles on a daily basis throughout the trial for safety purposes and for the purpose of insulin titration.

Conclusion

Subjects in this trial will benefit from an intensified insulin treatment in a basal-bolus regimen in a treat-to-target setting under close supervision.

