Hypoglycaemic episodes are classified according to the Novo Nordisk classification of hypoglycaemia (see Figure 2–1) and the ADA classification of hypoglycaemia (see Figure 2–2).

Novo Nordisk classification of hypoglycaemia

In normal physiology, symptoms of hypoglycaemia occur below a PG level of 3.1 mmol/L (56 mg/dL). Therefore, Novo Nordisk has included hypoglycaemia with PG levels below this cut-off point in the definition of BG confirmed hypoglycaemia.

Novo Nordisk uses the following classification (see Figure 2–1) in addition to the ADA classification:

- Severe hypoglycaemia according to the ADA classification.⁴
- Severe or BG confirmed hypoglycaemia: An episode that is severe according to the ADA classification⁴ or BG confirmed by a PG value <3.1 mmol/L (56 mg/dL) with or without symptoms consistent with hypoglycaemia.

[figure not shown]
Note: Glucose measurements are performed with capillary blood calibrated to plasma equivalent glucose values

BG: blood glucose PG: plasma glucose SMPG: Self-measured plasma glucose

Figure 2–1 Novo Nordisk classification of hypoglycaemia

ADA classification⁴ of hypoglycaemia

- Severe hypoglycaemia: An episode requiring assistance of another person to actively administer carbohydrate, glucagon, or take other corrective actions. Plasma glucose concentrations may not be available during an event, but neurological recovery following the return of PG to normal is considered sufficient evidence that the event was induced by a low PG concentration.
- Asymptomatic hypoglycaemia: An episode not accompanied by typical symptoms of hypoglycaemia, but with a measured PG concentration ≤ 3.9 mmol/L (70 mg/dL).
- Documented symptomatic hypoglycaemia: An episode during which typical symptoms of hypoglycaemia are accompanied by a measured PG concentration ≤ 3.9 mmol/L (70 mg/dL).
- Pseudo-hypoglycaemia: An episode during which the person with diabetes reports any of the typical symptoms of hypoglycaemia with a measured PG concentration > 3.9 mmol/L (70 mg/dL) but approaching that level.
- Probable symptomatic hypoglycaemia: An episode during which symptoms of hypoglycaemia are not accompanied by a PG determination but that was presumably caused by a PG concentration ≤ 3.9 mmol/L (70 mg/dL).

Note: Glucose measurements are performed with capillary blood calibrated to plasma equivalent glucose values PG: plasma glucose SMPG: Self-measured plasma glucose

Figure 2–2 ADA classification of hypoglycaemia

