Treatment emergent hypoglycaemic episodes are presented in terms of the number of subjects with at least one event (N), the percentage of subjects with at least one event (%), the number of events (E) and the event rate per 100 years of exposure (R). Separate summaries are made by severity considering all episodes, nocturnal and daytime episodes using Novo Nordisk and ADA classified episodes. All episodes will also be summarised by category, including summaries in relation to time since start of meal, as occurring within the following time intervals:

- During first 1, 2, and 4 hours after start of meal
- Between 1 (exclusive) to 2 hours (inclusive) after start of meal
- Between 2 (exclusive) to 3 hours (inclusive) after start of meal
- Between 3 (exclusive) to 4 hours (inclusive) after start of meal
- Between 2 (exclusive) to 4 hours (inclusive) after start of meal

The number of treatment emergent severe or BG confirmed hypoglycaemic episodes (all, daytime, nocturnal, 1 hour, 2 hours, 4 hours, 1 (exclusive) to 2 hours (inclusive), 2 (exclusive) to 3 hours (inclusive), 3 (exclusive) to 4 hours (inclusive), and 2 (exclusive) to 4 hours (inclusive) after start of the meal) will be analysed based on the FAS using a negative binomial regression model with a log-link function and the logarithm of the time period in which a hypoglycaemic episode is considered

Statistical Analysis Plan		Date:	12 February 2019	Novo Nordisk
Trial ID: NN1218-4113	CONFIDENTIAL	Version:	2.0	
UTN: U1111-1180-0636		Status:	Final	
EudraCT No.: 2016-000878-38		Page:	25 of 29	

treatment emergent as offset. The model will include treatment, region and metformin use at baseline (Yes/No) as factors. To the extent where data allow, separate analysis will be performed for severe hypoglycaemic episodes (all).

Change from baseline in clinical evaluations 16 weeks after randomisation:

Physical examination

The physical examination parameters (head, ears, eyes, nose, throat, neck, respiratory system, cardiovascular system, gastrointestinal system incl. mouth, musculoskeletal system, central and peripheral nervous system, skin), and their change from baseline, will be summarised descriptively using the on-treatment period. All findings will be listed.

Vital signs

Vital signs include diastolic blood pressure, systolic blood pressure and pulse. The measurements will be summarised descriptively using the on-treatment period and both actual values as mean change and change from baseline.

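### Silent early post-meal lows are rarely checked for, so the all-episode and daytime hypoglycaemia ratios may lean slightly towards faster aspart; a symptomatic-episode sensitivity model is missing

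*SAP*

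**What the plan says.** SAP 2.4.2.2 fits negative binomial models to treatment emergent severe or BG confirmed episodes: all, daytime, nocturnal, and several windows after the start of a meal (first 1, 2 and 4 hours, 1-2, 2-3, 3-4 and 2-4 hours). An episode qualifies if it is severe or "BG confirmed by a PG value <3.1 mmol/L (56 mg/dL) with or without" symptoms. The factors are treatment, region and metformin use, with log time at risk as offset. For the descriptive tables, "All episodes will also be summarised by category, including summaries in relation to time since start of meal". SAP section 3 says that the 1-2, 2-3 and 3-4 hour windows were added to look further at safety.

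When glucose is measured is set in Protocol version 4.0:

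- Section 8.3.3 instructs subjects "to perform 4-point profiles every day from Visit 2 to Visit 30": before breakfast, lunch and the main evening meal, and at bedtime.
- The only scheduled post-meal check is at 1 hour ("60 minutes after the start of breakfast", and likewise for lunch and the evening meal). It is done only on the three days of a 7-9-7-point profile.
- Section 8.6.3 places these profiles before Visits 14, 22, 30 and 30A. The Visit 14 set precedes randomisation.
- Section 8.4.2 also requires a measurement whenever hypoglycaemia is suspected, and records for each episode whether it was symptomatic.

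On timing, section 18.1 reports from an earlier type 2 diabetes trial that a significantly higher rate of "hypoglycaemic episodes was seen during the first 2 hours after a meal for faster aspart".

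**The concern.** A low without symptoms enters the data only if glucose happens to be measured. In the first 2 hours after a meal it seldom is; before the next meal and at bedtime it is measured every day. If one insulin moves lows from regularly checked times to rarely checked ones, some silent lows drop out of its count. A common schedule and blinding do not cancel this for the all-episode or daytime ratio, because the arms are expected to differ in when lows occur. The direction favours faster aspart.

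Silent lows are to be expected: impaired awareness of hypoglycaemia is recorded at screening (Protocol 8.2.3) and is not an exclusion (Protocol 6.3). The models have no term for measurement opportunity, and neither SAP 2.4.2.2 nor SAP 2.5 contains a modelled analysis that addresses it. At stake is how far an overall ratio near or below 1 can be read as no excess of hypoglycaemia.

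**Working it through.** The documents give no figure for detection by time since a meal, so there is none to reproduce. The schedule can be counted; the effect on the ratio needs assumptions.

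**Scheduled checks per subject** (full adherence, no Visit 30A)

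- "A 16-week treatment period" (Protocol 5.1): 16 × 7 = 112 days.
- Three main meals a day (Protocol 6.2): 112 × 3 = 336 meals.
- Daily profile: 112 × 4 = 448 checks.
- Profile days after randomisation: 2 visits × 3 days = 6, giving 6 × 3 = 18 checks at 60 minutes and 2 checks at 4 am.
- Total: 448 + 18 + 2 = 468.
- Certain to fall in the first 2 hours: 18/468 = 3.8% of checks, covering 18/336 = 5.4% of meals.

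**First 4 hours.** The pre-lunch, pre-dinner and bedtime checks each follow a meal at an interval the documents do not state. The share of checks within 4 hours of a meal is 18/468 = 3.8% if none of the three falls inside; 130/468 = 27.8% if one does; 242/468 = 51.7% if two do; and 354/468 = 75.6% if all do. The count therefore supports a statement about 2 hours, not 4.

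**Effect on the all-episode ratio.** Let p be the true share of lows in the first 2 hours (pC for NovoRapid, pT for faster aspart), s the symptomatic share, and q the chance that a scheduled check finds a later silent low. Symptomatic lows are taken as always recorded.

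- Early detection: dE = s + (1 − s) × 18/336
- Later detection: dL = s + (1 − s) × q
- Observed ratio when the true ratio is 1: [pT·dE + (1 − pT)·dL] / [pC·dE + (1 − pC)·dL]

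Example with pC = 0.10, pT = 0.15, s = 0.5, q = 0.5: dE = 0.5 + 0.5 × 0.0536 = 0.527 and dL = 0.75. The ratio is (0.15 × 0.527 + 0.85 × 0.75) / (0.10 × 0.527 + 0.90 × 0.75) = 0.7165/0.7277 = 0.985.

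Over s = 0.3, 0.5, 0.8 and q = 0.25, 0.5, 0.9 (all assumed):

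| Early share, NovoRapid vs faster aspart | Observed all-episode ratio |
|---|---|
| 5% vs 8% | 0.980 to 0.9986 |
| 10% vs 15% | 0.966 to 0.998 |
| 20% vs 30% | 0.927 to 0.995 |

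The lowest value needs 20% vs 30%, only 30% of lows symptomatic, and 90% of later silent lows found: dE = 0.3375, dL = 0.93, ratio 0.7523/0.8115 = 0.927.

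**Within one window.** The same dE applies in both arms, so the observed ratio is pT·dE/(pC·dE) = pT/pC, which is the true ratio. Events and precision are lost, but the ratio is not shifted.

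**Across windows.** In the example, the early window records 0.527 of its lows and later times 0.75. Within one arm, the early rate then looks 0.527/0.75 = 0.70 of its true size relative to the later rate. In addition, Protocol 8.4.2 dates an episode from the first low value or symptom, so an early silent low that lasts until the next check is assigned to a later window.

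**The case against.** Four points on the other side carry weight.

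- Severe and symptomatic early lows are captured, because measurement is required on suspicion. Only silent lows can be lost. This stands.
- An early excess on faster aspart would appear in the window models, whose ratios the schedule alone does not bias. This stands, provided that the symptomatic share is similar in the two arms. It does not repair the all-episode and daytime ratios.
- ADA classes, including documented symptomatic episodes, are already summarised by arm, with summaries by time since meal. This stands as far as it goes: those tables use 3.9 mmol/L rather than 3.1, and nothing symptomatic is modelled.
- The bias requires displaced lows to come from well-checked times. Protocol 18.1 describes only a slight shift and does not say from when. If the lows move from, say, 2-3 hours, which may also be mostly unchecked, the effect is smaller than computed here. This stands, and is one reason to call the bias possible rather than established.

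A reader might infer that the whole first 4 hours go almost unchecked. The documents do not show that, because no meal-to-check intervals are given. A reader might also infer that the early-window ratios are distorted in favour of faster aspart; with one schedule for both blinded arms, that does not follow.

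**Conclusion.** The point holds in limited form. Scheduled checks are nearly absent in the first 2 hours after a meal, the modelled endpoint includes silent lows, and no planned model deals with the unequal detection. If faster aspart shifts lows into those 2 hours, the all-episode and daytime ratios may be biased slightly in its favour, and patterns across windows partly reflect when glucose was measured.

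The size cannot be determined from the documents. Protocol 3.1.3 calls the first-2-hour episodes in the earlier trial a small part of the total. With assumed early shares of 5 to 15%, a true ratio of 1 appears as 0.966 to 0.9986, a distortion of about 0 to 3%. That trial's measuring schedule is not given, so its early share may itself be under-counted. A reader might take 0.93 as the likely distortion, but it needs a large early share together with few symptomatic lows and very good late detection, which fits poorly with a slight shift and a small early share.

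Nor do the documents make this a threat to a confirmatory claim: hypoglycaemia is a supportive secondary safety endpoint outside the testing hierarchy. The change is worth making because it is cheap and gives a ratio that depends much less on the check schedule.

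**What to change.** In SAP 2.4.2.2, add a sensitivity analysis. Repeat the negative binomial model, with the same analysis set, factors and offset, for episodes that are severe or are symptomatic with plasma glucose below 3.1 mmol/L. Do this for all and for daytime episodes and, where data allow, for each post-meal window. State that the overall ratio will be read together with this result. The planned summaries of ADA documented symptomatic episodes stay as they are.

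Symptom status is already part of each episode record (Protocol 8.4.2). The same section says that the sponsor will not query symptom status for non-severe lows whose form was not completed within 7 days, so the SAP should state how missing symptom status is handled and report its frequency by arm.

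The cost is SAP wording and extra output, with fewer events and wider intervals in the symptomatic models.

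A table of low laboratory glucose values at the Visit 30 meal test is optional and supportive only. It covers one meal at the baseline bolus dose, starts from a restricted glucose range, allows glucose rescue that alters later samples (Protocol 8.3.1), and used a different meal volume in three countries (SAP 2.5).
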